7.2.2 Other Data Processing Rules

In the descriptive summaries of safety endpoints (e.g., absolute value and change from baseline in laboratory tests, vital signs, ECG), if an assessment is measured two or more times at a visit, then the last data of the visit will be used for analysis. The assessment results of all unscheduled and scheduled visits will be presented in the listings.

7.2.3 Derived Dates

Study Days

Refer to Protocol Section 4.3 for the schedule of assessments. Study Days are calculated from the LTT start date as follows:

- Assessment/event date/eDiary reference date – LTT start date + 1, if the assessment/event date \geq LTT start Date;
- Assessment/event date/eDiary reference date – LTT start date, if the assessment/event date $<$ LTT start Date, where

LTT start date is defined as earlier of (1) Baseline Visit date, or (2) study drug start date (see also in Section 7.2.4).

Treatment Days

Treatment days are calculated from the study drug start date as follows:

- Assessment/event date – study drug start date + 1, if the assessment/event date \geq study drug start date.
- Assessment/event date – study drug start date, if the assessment/event date $<$ study drug start date.

The Treatment Day will be displayed together with Study Day in the individual participants listings.

eDiary Days

An eDiary day is defined as a day with a complete eDiary reference date based on any question from the evening report headache log or follow up log (see step b.iv in [Appendix: the derivation of migraine day](#)).

Last Contact Date

The last contact date is used to determine select parameters (i.e., time on study, imputed non-study medication end dates), and is typically defined using non-imputed dates as follows:

1. Earliest complete death date from all sources that collect death dates (e.g., Death CRF), if it exists.
2. Otherwise, the maximum complete date of the following CRF or external data sources, as applicable: AE start or end; ECG; eDiary assessment; informed consent; laboratory test collection; non-study medication start or end; physical exam; protocol deviation;

questionnaire; rating scale; study intervention start or end; participant disposition completion/discontinuation; visit; vital signs.

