**Table 1. Assessment Schedule**

Procedure	Screening Visit	Observational Period (30 days, ±2 days)	Baseline Visit (Day 1)	Phone visit to confirm eligibility based on Clinical Laboratory Findings	Weeks 4, 8, 12 (all visits ±3 days)	Weeks 16, 28, 40, 52 (or Early Termination) (all visits ±7 days)	Phone visits Weeks 20, 24, 32, 36, 44, 48(all visits ±7 days)	Follow-up Safety Visit (14 days after EOT visit ±2 days)
Preference of Medication (PoM)						X (Weeks 28 and 52/early termination only)		
Satisfaction with Medication (SM) Survey						X (Weeks 28 and 52/early termination only)		
Clinical Global Impression – change (CGI-c)						X (Weeks 28 and 52/early termination only)		
Migraine Disability Assessment (MIDAS)			X		X (Weeks 12 only)	X (Weeks 28, 40 and 52/early termination only)		

1. Eligibility must be confirmed based on clinical laboratory test results at baseline and migraine occurrence during the observational period before the first dose of study drug. Site staff must notify participants by telephone of study eligibility before the participant takes his/her first dose of study drug.
2. All concomitant medications, including prophylactic and standard of care migraine medications, as well as medications taken during the observation and Long-Term Treatment Periods, should be recorded via BYOD and reviewed by study personnel at each study visit.
3. Collect required concomitant medications due to AEs and collect concomitant medications associated with AEs.
4. Height will be measured at the Screening Visit only. Participant weight, temperature, respiratory rate, blood pressure, will be collected at all time points indicated. Sitting systolic and diastolic arterial blood pressure and pulse rate will be measured.
5. If the participant has confirmed the status of WOCBP in the BHV3000-310 trial, the participant is acknowledged to have the same status in this study.

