#### **4.3.2. Long-term Treatment Period (52 weeks)**

After completing the 30-day Observation Period, the participants will return to the clinical site for the Baseline Visit (Day 1). The main operations or examinations to be completed by the participants included:

- Evaluation of inclusion/exclusion criteria;
- Recording prophylactic and standard of care migraine medications/concomitant medications via BYOD;
- Physical examination;
- Vital signs/physical measurements;
- Clinical safety laboratory tests;
- Lipid panel
- ECG;
- Urine routine;
- Pregnancy test (urine and serum);
- AE and SAE assessments;
- Dispense study drug;
- Return eDiary and review eDiary and BYOD of completion for completeness;
- Daily recording of migraine attacks and their severity by eDiary;

- MSQoLQ version 2.1;
- MIDAS.

After the completion of the relevant items at the Baseline Visit (Day 1), before the participants take the study drug for the first time, the clinical site staff should confirm the eligibility of the participants for participating in the study based on the examination results at the Baseline Visit, and inform the participants by telephone of the eligibility results. The participants who meet all the inclusion criteria and do not meet the exclusion criteria can participate in the trial. Participants confirmed to be eligible by a telephone visit may start taking the study drug, rimegepant 75 mg (up to 1 tablet per day) at the time of a migraine attack (mild, moderate, or severe) and record the use of the study drug with BYOD.

Participants will make site visits at Weeks 4, 8, 12 ( $\pm 3$  days) and Weeks 16, 28, 40, 52 ( $\pm 3$  days) or Early Termination of the trial and telephone visits at Weeks 20, 24, 32, 36, 44, 48 for the Long-Term Treatment Period as follows:

- Recording prophylactic and standard of care migraine medications/concomitant medications via BYOD;
- Physical examination (Weeks 28 and 52 or early termination);
- Vital signs/physical measurements (at each site visit);
- Clinical safety laboratory tests (at each site visit);
- Lipid panel (at Weeks 28 and 52 or early termination);
- Electrocardiogram (at Weeks 28 and 52 or early termination);
- Urine routine (Week 52 or early termination);
- Urine pregnancy (at each site visit and at each telephone visit);
- AE and SAE assessments (at each site visit and at the telephone visit);
- Dispense study drug (at each site visit);
- Take the study drug;
- Record the use of study medication via BYOD;

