## 5.5. Prophylactic and Standard of Care Migraine Medications

Participants using prophylactic migraine medications are permitted to remain on therapy if the dose has been stable for at least 2 months prior to the Baseline Visit and this dose is not expected to change during the study. Participants who previously discontinued prophylactic migraine medication must have done so at least 5 half-lives of the prophylactic medication prior to the Screening Visit.

Participants may need to take previously prescribed standard of care medications: aspirin, ibuprofen, acetaminophen (including Excedrin®Migraine) up to 1000 mg/day for a maximum of 2 consecutive days at a time, naproxen (or any other type of non-steroidal anti-inflammatory [NSAID]), antiemetics (eg, metoclopramide or promethazine), or muscle relaxants, which are used during the study (Observation Period and Long-Term Treatment Phase) for the standard of care treatment of migraine.

Use of triptans by participants without a contraindication to their use is allowed during the Observation Phase but must be discontinued at the Baseline Visit. As described above, use of triptans is prohibited during the Long-Term Treatment Phase. With the exception of triptans described in this section, participants are allowed to take standard treatment for migraine during the study, if needed, but are required to meet dose restrictions if taking acetaminophen (no more than 1000 mg/day at a time for 2 consecutive days).

If a participant takes a tablet of study drug and experiences a migraine later that day, the participant can take standard of care medications for migraine (as described in this section above) after taking the study drug that day. Participants are not allowed to take more than 1 tablet of the study medication per calendar day.

Use of standard of care medications during Observation Period and Long-Term Treatment Phase, will be recorded by the participant via BYOD and reported to the site.

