#### **6.1.4. Clinical Laboratory Tests**

##### **6.1.4.1. Safety Laboratory Testing**

Blood and urine samples for clinical laboratory assessments will be collected as outlined in [Table 1](#). A central laboratory vendor will be utilized for this study and a laboratory manual will be provided to each site. If possible, participants should be fasting for a minimum of 8 hours before each blood draw. However, if the participant is not fasting at the specified visit, the participant should still have blood drawn and the non-fasting status should be documented.

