6 ANALYSIS SETS

The following analysis sets will be determined:-

- Screened participants set: All participants who sign the informed consent. It will be used for the analysis of participant disposition.
- Enrolled participants set: Participants with an available date collected in the CRF on

which the investigator judges that they can be enrolled and notifies of their eligibility to start taking the investigational product by phone. It will be used for the analysis of participant disposition and drug accountability.

- Full analysis set (FAS): All participants who are enrolled and received at least one dose of the investigational product. It will be used for the analysis of baseline characteristics, as well as the analyses of exploratory endpoint measures.
- Efficacy analysis set (EAS): All participants in the FAS with ≥ 14 eDiary days (not necessarily consecutive) in both the OP analysis period and ≥ 1 month (4-week interval) of the LTT analysis period. The EAS will be used to assess the secondary endpoint.
- Safety analysis set (SS): All participants who received at least one dose of investigational product. The SS will be used for safety analyses during treatment safety period.
- Follow-up safety analysis set (FUSS): All participants in the SS with last contact date (see [Section 7.2.3](#)) in the follow-up safety analysis period. The FUSS will be used for follow-up safety analyses.

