7.2.5 Analysis Visit Windows

According to Section 4.3 of the protocol, the analysis visit windows for efficacy analyses will be defined. Analysis windows for the secondary endpoint will be defined within the OP and LT_T analysis periods that are defined in Section 7.2.4 (See [Table 2](#)[Table 2](#)). The calculation of number of migraine days will be based on the study day as defined in Section [Error! Reference source not found.](#)[7.2.3](#). Analysis windows for the exploratory endpoints will be defined directly as below in [Table 3](#)[Table 3](#).

Table 2. Analysis Windows for Migraine Days

Per 4-week Interval	Analysis Window in the LT _T Analysis Period (Study Day)
Month 1: Week 1 to Week 4	1-28

Month 2: Week 5 to Week 8	29-56
Month 3: Week 9 to Week 12	57-84
Month 4: Week 13 to Week 16	85-112
Month 5: Week 17 to Week 20	113-140
Month 6: Week 21 to Week 24	141-168
Month 7: Week 25 to Week 28	169-196
Month 8: Week 29 to Week 32	197-224
Month 9: Week 33 to Week 36	225-252
Month 10: Week 37 to Week 40	253-280
Month 11: Week 41 to Week 44	281-308
Month 12: Week 45 to Week 48	309-336
Month 13: Week 49 to Week 52	337-end of LTT

Table 3. Analysis Windows for MSQoLQ, MIDAS, PoM, SM, and CGI-c Scale

Scheduled Visits *	Target Day (Based on Study Day)	Analysis Window (Study Day)
Baseline	1	Prior to or on the first dose date
Week 12	84	71-98 #
Week 28	196	183-210 #
Week 40	280	267-294 #
Week 52	364	351- end of LTT
Early Termination	The Early Termination Visit or last post-baseline questionnaire from the early terminated participants	

* The PoM, SM, and CGI-c scale will not be collected at baseline, Week 12 and Week 40.

For early terminated participants, the Week X window end date will be the minimum of (1) Early Termination Date -1 day or (2) Week X analysis window end date, where X is the last Week with Target Day being prior to Early Termination Date.

In [Error! Reference source not found.](#)[Table 3](#), if there are multiple non-missing values fall into a same analysis windows, then the following algorithm will be taken to identify the value for analysis:

1. The value closest to the target day for the visit will be used.
2. If the observations are with equal distance from the target day in absolute value, the one with correct nominal visit label will be used. For example, if two observations fall into the analysis window for Week 28 Visit on Study Days 190 and 202, respectively, the observation that is recorded as Week 28 will be used.

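### The SAP starts long-term treatment at the Baseline Visit, so any days before telephone clearance to dose count as treatment in Month 1, the overall rate and the tablets-per-month denominator

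*SAP*

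**What the plan says.** **SAP.** Section 7.2.3 fixes the start of LTT: "LTT start date is defined as earlier of (1) Baseline Visit date, or (2) study drug start date". Table 1 in 7.2.4 repeats this and ends the Observation Period (OP) the day before. Study Day counts from that date. In Table 2 (7.2.5), "Month 1: Week 1 to Week 4" is Study Days 1-28. The overall LTT migraine-day rate (7.4.1) and the time in LTT (7.5.1) start on the same date. Average tablets per month divides by time in LTT, and its classes (cut-points 2, 8 and 14) stratify the adverse event, laboratory, vital sign and ECG abnormality tables in 7.5.2 to 7.5.5.

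**Protocol.** Table 1, footnote 1, sets the order of events: "Eligibility must be confirmed based on clinical laboratory test results at baseline", and "Site staff must notify participants by telephone of study eligibility before the participant takes his/her first dose of study drug". Section 4.3.2 agrees: "Participants confirmed to be eligible by a telephone visit may start taking the study drug". In Table 1, administration of study medication is first marked in the telephone-visit column, not at Baseline. Section 6.1.4.1 adds: "A central laboratory vendor will be utilized for this study". Under 5.5, triptans are allowed in the OP "but must be discontinued at the Baseline Visit".

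**The clearance date exists.** SAP 6 defines the Enrolled set by a CRF date on which the investigator judges the participant enrollable and "notifies of their eligibility to start taking the investigational product by phone".

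**The concern.** The secondary endpoint is the change in migraine days during treatment with rimegepant, relative to the OP. Days on which rimegepant is not yet permitted do not belong to that treatment period. They do not match the OP either, because triptans have already stopped.

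Three results depend on how these days are handled:

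- **Month 1.** The first point of the 13-month curve may mix days before and after permission to dose.
- **The 14-eDiary-day rule.** A participant with 7 diary days before clearance and 7 after it reaches 14. That is enough for Month 1 and for entry to the Efficacy Analysis Set, on only 7 treatable days.
- **Exposure classes.** The denominator of tablets per month includes days when no tablet could be taken, which lowers the average.

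The SAP is not uniform here. Its treatment safety period (7.2.4) and its time on rimegepant (7.5.1) start at first dose, while the strata used to tabulate the same safety data run from the Baseline Visit.

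**Working it through.** **1. The plan's own figure.** Inputs from Protocol 10.2 and SAP 3.4: change -1.08, SD 4.74, one-sided 2.5%, 90% power, 12% dropout. A one-sample t test with noncentral t power needs n = 205 (power 0.901; the normal approximation gives 203), and 205/0.88 = 232.95, so 233. For the interim analysis (Protocol 10.3), n = 154 gives power 0.802, and 154/0.88 = 175. All of these reproduce. They rest on Weeks 9-12, which is Study Days 57-84. These days lie after clearance for any gap up to 56 days, so the sizing is untouched.

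**2. The gap.** Let g be the number of days from Baseline Visit to clearance. Study Days 1 to g are then pre-clearance. No document gives g. I assume 1 to 10 days; g = 0 if clearance comes on the visit day.

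- Share of Month 1 = g/28.
- Share of a full LTT = g/364 (52 x 7 days).
- Reported tablets per month = rate since clearance x (T - g)/T, where T is days in LTT.

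| g (days) | Share of Month 1 | Share of 364 days | Rate of 14, completer (T = 364) | Rate of 14, T = 28 |
|---|---|---|---|---|
| 0 | 0% | 0% | 14.00 | 14.00 |
| 1 | 3.6% | 0.3% | 13.96 | 13.50 |
| 3 | 10.7% | 0.8% | 13.88 | 12.50 |
| 7 | 25.0% | 1.9% | 13.73 | 10.50 |
| 10 | 35.7% | 2.7% | 13.62 | 9.00 |

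**3. Who changes exposure class.** Among completers with g = 7, only rates just above a cut-point move down a class: from 14 up to 14 x 364/357 = 14.27, or from 8 up to 8 x 364/357 = 8.16. Early discontinuers can move further. Take g = 7, then 10 tablets in 14 days, with LTT ending that day. The SAP gives 4 x 10/3 = 13.3 (class 8 to <14). Counted from clearance it is 4 x 10/2 = 20 (class 14 or more). This case is deliberately extreme.

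**4. Month 1 migraine days, one scenario.** Suppose the change is -1.08 once dosing is permitted and gap days stay at the OP level. Month 1 then shows -1.08 x (28 - g)/28: -1.04, -0.96, -0.81 and -0.69 for g = 1, 3, 7 and 10. Overall LTT, with 364 in place of 28, still shows -1.05 at g = 10.

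**5. Why the direction is open.** Step 4 needs gap days to behave like OP days, and they may not. Triptan use makes a day a migraine day automatically, and so does study-drug use in LTT (SAP 8.1, part II). With triptans stopped and rimegepant not yet allowed, a gap headache normally has to meet the duration and feature criteria. Gap days could therefore yield fewer counted migraine days and make Month 1 look better.

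**The case against.** The strongest defence is that the SAP follows the protocol's own labels. Protocol Table 1 calls the Baseline Visit Day 1, section 4.3.2 on the 52-week treatment period opens with it, and drug is dispensed there. Analysing an as-needed regimen from dispensing is a recognisable convention. This explains the choice, but it does not turn days on which the protocol withholds the drug into treatment days. Days after clearance spent waiting for a first attack are different: they are part of as-needed use and belong in LTT.

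Other parts of the defence stand:

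- The size is assumed. The documents give no laboratory turnaround and do not rule out same-day clearance. A reader might infer that every participant has a gap, but the text supports only that no one may dose before clearance.
- The gap days are not wholly untreated. Protocol 5.5 allows NSAIDs, acetaminophen within limits, antiemetics and muscle relaxants throughout.
- A reader might infer that the Month 1 effect is diluted by exactly g/28 and that the step from Month 1 to Month 2 is an artefact. Neither is established, for the reason in step 5.
- The analysis is descriptive. The primary safety classification starts at study drug start and is not affected.

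**Conclusion.** The point holds, with limited reach. The LTT start date admits pre-clearance days to Month 1, to the overall LTT rate and to the tablets-per-month denominator. On the assumed gap of 1 to 10 days they are 4% to 36% of Month 1 and 0.3% to 2.7% of a full LTT. Material effects are confined to Month 1 and to the exposure class of early discontinuers or of participants close to a cut-point. The direction of any Month 1 bias cannot be determined from the documents.

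Months 2 to 13 contain no gap days for any gap up to 28 days. The classification of treatment-emergent events, time on rimegepant, Weeks 9-12 and N = 205/233 are unaffected. A reader might infer that the whole treatment curve or the primary safety results are compromised; the documents do not support that. If clearance always came on the day of the visit, the effect would be nil.

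**What to change.** Keep Study Day, the Table 2 and Table 3 windows and the end of the OP as they are, and make three changes:

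1. **SAP 7.4.1.** Exclude diary days before the eligibility-notification date in the CRF (or before first dose, if earlier) from numerator and denominator of Month 1 and overall LTT, and from the count of 14 eDiary days, including where that count decides entry to the Efficacy Analysis Set. The existing proration to 28 days handles the shorter window.
2. **SAP 7.5.1.** Start the time denominator for average tablets per month at that same date, and apply the two-week rule in that formula to the same time. State a fallback for anyone treated without a notification date, a category that SAP 7.3.1 foresees.
3. **Reporting.** Tabulate the distribution of the Baseline-to-clearance interval, so that readers can see whether the issue had any size.

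Two other repairs are worse. Anchoring on first dose would open Month 1 with a migraine day by rule, because a study-drug day counts as one. Moving Study Day 1 to clearance would shift the Table 3 windows against the visit calendar and shorten Month 13. With a Week 52 visit 7 days early (Day 357), Month 13 now has 357 - 337 + 1 = 21 days; it would have 14 after a 7-day shift and 11 after a 10-day shift, against a minimum of 14 diary days.

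The cost is SAP wording and one date that is already collected. A few Month 1 diary days per participant go unused, and a few participants may fall below 14 eDiary days in Month 1.

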## **6.7. Early Withdrawal Criteria**

Participants who meet the following criteria will be withdrawn from the study:

- Poor participant compliance and inability to comply with the study protocol;
- Participant lost to follow-up;
- The participant withdraws consent and requests withdrawal from the study and subsequent follow-up.

During the trial, the participant may decide to withdraw from the trial treatment and late follow-up for any reason at any time. After the participant decides to withdraw, the investigator should record the information of withdrawal event of the participant, including at least withdrawal date and reason. Lost to follow-up is defined as failure to contact the participant after 3 times of telephone calls or other methods, such as mail/registered mail/express mail. The investigator should record the specific situation of lost to follow-up, including at least the date and way of trying to contact.

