7.2.4 Analysis Periods

To facilitate the analyses based on eDiary data (including eDiary compliance and migraine days), the analyses for safety endpoints, the following analysis periods will be defined.

Table 1. Analysis Periods

Analysis periods	Start date/time	End date/time	Usage
OP	Screening Visit date	LT _T start date – 1 day	To be used to calculate the eDiary compliance, number of migraine days per 4 weeks in this period.
LT _T	Earlier of (1) Baseline Visit date, and (2) study drug start date	Later of (1) Week 52/EOT date, and (2) study drug last dose date	To be used to calculate the eDiary compliance and number of migraine days per 4 weeks or the overall period in the long-term treatment.
Pre-treatment safety		Study drug start date – 1 day for AEs; study drug start date/time otherwise	To be used to assess the safety endpoints prior to study drug treatment.
Treatment safety	Study drug start date for AEs; after study drug start date/time otherwise	[Later of (1) Week 52/EOT date, and (2) study drug last dose date] + 7 days	To be used to assess the safety endpoints of the treatment period.
Follow-up safety	[Later of (1) Week 52/EOT date, and (2) study drug last dose date] + 8 days		To be used to assess the safety endpoints of the follow-up period.

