- The original E5 “eDiary or BYOD not completed per protocol (to be assessed as Major in case of eDiary missing for 6 or more times a month)” corresponds to 6) -2. The original E6 corresponds to 6) -5 if with the keywords “contraception” or “pregnancy” in the PD description, or to 6) -2 “study procedure or examination (eDiary completion, ECG, physical examination, questionnaire, rating scale, etc.) not done per protocol” if without the above key words. The original F2 “Visit missing” corresponds to 5) -2 “Visit missing (to be regarded as Important if the missing visit has had an important impact on study results, e.g., leading to safety data missing for more than 12 weeks or withdrawal from visit)”.
- The original J1 “Not fitting into any of the above categories” corresponds to 10) -1 “No standard sub-categories”.

The recommended rules for mapping the of categorization of Minor PDs due to COVID-19

to the new categorization of Non-Important PDs due to COVID-19 are as follows:

- The original F1 “Visit out of allowable window” corresponds to 5) -1 “Visit not performed per protocol (visit out of window)”.
- The original F2 “Visit missing” corresponds to 5) -2 “Visit missing (to be regarded as Important if the missing visit has had an important impact on study results, e.g., leading to safety data missing for more than 12 weeks or withdrawal from visit)”.
- The original E-3 “Other laboratory tests, physical examination, vital signs, questionnaire, or other protocol-specified procedures missing” corresponds to 6) -3 “Study procedure or examination missing or incomplete (for indicators concerning the assessment of eligibility criteria or primary endpoint, if the procedure/examination has had an important impact on study results, e.g., where the procedure/examination was missing for more than 12 consecutive weeks, it would be regarded as Important)” if with the keyword “vital signs” in the PD description, or to 4) -4 “Lab test not done (for indicators concerning the assessment of eligibility criteria or primary endpoint, if the test has had an important impact on study results, e.g., where the test was missing for more than 12 consecutive weeks, it would be regarded as Important)” if without the above keyword.
- The original E-4 “Lab test or other procedure out of protocol-specified window” corresponds to 6) -2 “study procedure or examination (eDiary completion, ECG, physical examination, questionnaire, rating scale, etc.) not done per protocol”.

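### Protocol-deviation and disposition dates count as last contact, so a treated participant with no follow-up data can enter the follow-up safety set and lower its adverse-event percentages

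*SAP*

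**What the plan says.** SAP section 6 defines FUSS as "All participants in the SS with last contact date" in the follow-up safety analysis period, and adds: "The FUSS will be used for follow-up safety analyses". No visit, sample or AE inquiry in that period is required.

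SAP 7.2.3 sets the last contact date to the death date if there is one. If not, it is given by this rule: "Otherwise, the maximum complete date of the following CRF or external data sources, as applicable". The list contains "non-study medication start or end; physical exam; protocol deviation" and closes with "participant disposition completion/discontinuation; visit; vital signs". The SAP does not say which date of a deviation is meant (occurrence or recording), or what a discontinuation date represents when the participant could not be reached.

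SAP 7.2.4 (Table 1) starts the follow-up safety period at "Later of (1) Week 52/EOT date, and (2) study drug last dose date] + 8 days" and gives no end date. The scheduled Follow-up Visit is 14 ± 2 days after end of treatment (Protocol 4.1).

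SAP 7.5.2 uses FUSS for the follow-up AE tables. SAP 7.5.3 to 7.5.5 use it for follow-up laboratory, vital-sign and ECG abnormality counts and percentages.

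**The concern.** Two of the listed sources can record that contact failed. A missed visit is a deviation category of its own in SAP 8.2, which grades it by whether it has an important effect, for example "leading to safety data missing for more than 12 weeks or withdrawal from visit". Loss to follow-up, under Protocol 6.7, is declared once three attempts to reach the participant have failed. If either event carries a date inside the follow-up period, the rule treats the absence of contact as contact.

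The participant then sits in the denominator of the follow-up AE tables and cannot contribute to the numerator, because nobody asked about events. The bias is always downward, and it is largest where follow-up was poorest. It is a small bias in descriptive tables, but it follows from applying the written rule exactly as it stands.

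**Working it through.** **1. The chain of definitions**

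| Step | Source | Rule |
|---|---|---|
| Membership | SAP 6 | In the safety set, with last contact date in the follow-up safety period |
| Last contact date | SAP 7.2.3 | Latest complete date over a list that includes deviations and disposition |
| Period | SAP 7.2.4 | From +8 days after the later of EOT and last dose, open-ended |
| Missed visit | SAP 8.2 | A protocol deviation |
| Lost to follow-up | Protocol 6.7 | Defined by failed contact attempts |
| Screen for follow-up data | none found | – |

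The Follow-up Visit window is EOT + 12 to EOT + 16 days (14 − 2 and 14 + 2), which lies inside a period that opens at + 8. A deviation dated to a missed Follow-up Visit would therefore be enough for entry. So would a lost-to-follow-up disposition dated at + 8 days or later.

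**2. Which outputs are exposed**

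- Follow-up AE, SAE and fatal-AE percentages (SAP 7.5.2): exposed. A participant who was never asked has no recorded event and counts as event-free.
- Follow-up laboratory, vital-sign and ECG abnormality percentages (SAP 7.5.3 to 7.5.5): exposed only if all of FUSS is the denominator. The SAP does not say. For PoM, SM and CGI-c it does limit the denominator to participants with data (SAP 7.4.2).
- By-visit summaries at the Follow-up visit (SAP 7.5.3 to 7.5.5): not exposed, because they use the safety set.
- Treatment-period TEAE tables: not exposed, because they use the safety set and a period that ends at + 7 days.

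**3. Size**

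The documents give no FUSS size, no count of missed follow-up visits and no follow-up AE rate, so there is no planned figure to reproduce. Two planning figures are borrowed to set a range: 240 participants, and a 12% dropout allowance (Protocol 10.2, SAP 3.4). The allowance is internally consistent: 205 / (1 − 0.12) = 232.95, rounded up to 233. Applied to 240 it gives 0.12 × 240 = 28.8, about 29.

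Let N be the FUSS size and m the number of members who are there only through an administrative date. Then

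reported rate = true rate × (N − m) / N, and relative understatement = m / N.

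With N = 240 (assumed):

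| m (assumed) | m / N | true 5% reads | true 10% reads |
|---|---|---|---|
| 2 | 0.8% | 4.96% | 9.92% |
| 5 | 2.1% | 4.90% | 9.79% |
| 12 | 5.0% | 4.75% | 9.50% |
| 24 | 10.0% | 4.50% | 9.00% |
| 29 | 12.1% | 4.40% | 8.79% |

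The follow-up AE tables are also split by average exposure category. Within a category, the understatement is that category's own m/n, which may be above or below the overall figure.

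**The case against.** The best case on the other side has several parts.

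*Dating.* Neither document says that a missed-visit deviation is dated at or after the planned visit, or that a lost-to-follow-up disposition carries the date of the last failed call. This stands. It governs how many participants enter by this route, not whether the rule lets them in.

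*Disposition dates can be real contact.* When Protocol 6.7 asks the investigator to record a withdrawal, "including at least withdrawal date and reason", it concerns a participant who has decided to leave, and telling the site so is normally contact. This stands, and it is why disposition dates should not be struck out wholesale.

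*The 12% is not a missed-visit rate.* It comes from BHV3000-201 and was used to reach 205 evaluable participants for migraine days at Weeks 9-12. Protocol 6.6 also asks that participants who stop treatment make every effort to complete later safety visits, and Protocol 4.3.3 provides an end-of-treatment visit at early termination. So m = 29 is an upper bound for illustration: it needs every dropout both to lack follow-up contact and to carry a late administrative date.

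A reader might infer that every follow-up rate is diluted. The documents do not support that. The by-visit summaries use the safety set, and the denominator of the abnormality percentages is left open. The missing category promised in SAP 7.1 would make absent assessments visible, although it would not by itself take them out of the denominator.

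A reader might also infer that an inflated time on study distorts the results. SAP 7.2.3 names that parameter, but no specified table uses it; the exposure summaries in SAP 7.5.1 rest on other dates.

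**Conclusion.** The point holds in a limited form. As written, SAP 6 and 7.2.3 allow a treated participant with no follow-up visit, measurement or AE inquiry into FUSS, and nothing later in the SAP removes that participant. The follow-up AE, SAE and fatal-AE percentages are then understated in proportion to the number of such members.

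The size cannot be derived from the documents. It rests on an assumed FUSS of 240, an assumed m between 2 and 29, and administrative dates that fall in the period. Under those assumptions the effect runs from negligible to about one eighth in relative terms.

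Numerators do not change, all AEs are listed with a follow-up flag, no hypothesis is tested, and the main safety result is untouched. This is a definition worth correcting, not a threat to the trial's conclusions.

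**What to change.** Change the rule for FUSS membership only, leaving the last contact date as it is for its other uses:

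1. Disregard protocol-deviation dates, and disposition dates that do not rest on actual contact (such as lost to follow-up).
2. Require at least one participant-derived date in the follow-up safety period: a visit, laboratory sample, ECG, vital signs, AE report or other documented contact, including a withdrawal of consent that the participant communicated.
3. State that follow-up laboratory, vital-sign and ECG abnormality percentages use FUSS members with at least one value of that type in the period.

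The cost is a few sentences in SAP 6, 7.2.3 and 7.5.3 to 7.5.5, a small programming change and a slightly smaller FUSS. No new data collection is needed.
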